6.4 Day 0 (SB-913 Infusion)

Subjects will receive the SB-913 infusion at a hospital or acute care facility, remain there for at least 24 hours after the infusion for observation, and be discharged when all AEs and vital signs are stable.

- Review and record concomitant medications.
- Physical examination.
- Vital signs (for frequency, refer to the Study Reference Manual).
- Assessment of AEs.
- ERT administration log.
- Pregnancy test (females of childbearing potential only, and if >7 days from Baseline pregnancy testing).
- Prednisone or equivalent corticosteroid administration.
- Infusion of SB-913 via a peripheral vein catheter.

6.5 Day 1

All subjects will remain in the hospital or acute care facility for at least 24 hours after completion of SB-913 infusion. Subjects will be discharged when all AEs and vital signs are stable.

The following assessments and procedures will be performed:

- Review and record concomitant medications.
- Physical examination.
- Vital signs (continued measurement from Day 0).
- Assessment of AEs.
- Clinical laboratory tests.
- Liver panel.
- Vector genome PCR in plasma (12 hours after end of SB-913 infusion).
- Prednisone or equivalent corticosteroid administration.

6.6 Day 7 (+/- 1 day)

The following assessments and procedures will be performed:

- Review and record concomitant medications.
- Physical examination.
- Vital signs.
- Assessment of AEs.
- ERT administration log.
- 12-lead ECG.
- Liver panel.
- Vector genome PCR in plasma, saliva, urine, stool, and semen (males only).
- Prednisone or equivalent corticosteroid administration.

6.7 Weeks 2, 4, 6, and 8 (+/- 2 days)

The following assessments and procedures will be performed unless otherwise stipulated:

- Review and record concomitant medications.
- Physical examination.
- Vital signs.
- Assessment of AEs.
- ERT administration log.
- Pregnancy test (females of childbearing potential only; at Weeks 4 and 8 only).
- Clinical laboratory tests.

- Liver panel (twice weekly; may be conducted at home if subject is remote).
- GAG testing in urine.
- IDS / GAG testing in blood.
- Circulating AFP level (at Weeks 4 and 8 only).
- Vector genome PCR in plasma, saliva, urine, stool, and semen (males only) (at Weeks 2, 4, and 8 only).
- Immunogenicity assays (at Week 4 only).
- Prednisone or equivalent corticosteroid administration.

6.8 Weeks 12, 16, 20, 24, 28, 32, 36, 40, 44, 48, and 52 (+/-1 week)

The following assessments and procedures will be performed unless otherwise stipulated:

- Review and record concomitant medications.
- Physical examination (at Weeks 12, 16, 20, 24, 36, and 48 only).
- Vital signs (at Weeks 12, 16, 20, 24, 36, and 48 only).
- Assessment of AEs.
- ERT administration log.
- JROM (at Weeks 24 and 48 only).
- Neurologic cranial nerve exam and muscle strength testing of the upper extremities (at Weeks 24 and 48 only).
- 12-lead ECG (at Weeks 24 and 48 only).
- ECHO (at Week 48 only).
- Pregnancy test (females of childbearing potential only; at Weeks 12, 16, 20, 24, 36, and 48 only).
- Clinical laboratory tests (at Weeks 12, 16, 20, 24, 36, and 48 only).
- Liver panel (twice weekly until Week 20; then at Weeks 24, 28, 32, 36, 40, 44, 48, and 52; may be conducted at home if subject is remote until Week 20 and at Weeks 28, 32, 40, 44, and 52).
- GAG testing in urine.
- IDS / GAG testing in blood (at Weeks 12, 16, 20, 24, 36, and 48 only).
- Circulating AFP level (at Weeks 12, 24, and 48 only).
- Vector genome PCR in plasma, saliva, urine, stool, and semen (males only) (at Weeks 12, 16, 20, 24, 36, and 48 only).
- PFTs (at Weeks 24 and 48 only).
- 6MWT (at Weeks 24 and 48 only).

- Neurocognitive abilities tests by WASI-II, WPPSI-IV, or BSID-III, and by VABS-II (at Weeks 24 and 48 only).
- MRI of liver (at Weeks 24 and 48 only).
- MRI of brain and cervical spine (at Week 48 only).
- ACTH stimulation (cosyntropin) test (at Week 20 only or at end of prednisone or equivalent corticosteroid taper; see Appendix 3).
- Liver biopsy (at Weeks 24 and 48 only).
- Lumbar puncture (at Weeks 24 and 48 only).
- Immunogenicity assays (at Weeks 12, 24, 36, and 48 only).
- Prednisone or equivalent corticosteroid administration (through Week 20 only).

6.9 Months 15, 18, 21, 24, 27, 30, 33, and 36/End of Study (+/-1 month)

Subjects will be evaluated every 3 months in Years 2 and 3 after SB-913 infusion.

An End of Study (EOS) visit will be conducted at Month 36.

At the EOS visit, subjects will be asked to participate in the LTFU Study. Study subjects may participate in the LTFU Study after 12 months of follow-up in this study, in which case an EOS visit may be conducted anytime after Week 52 but before the next scheduled study visit.. Study participants who wish to enroll in the LTFU Study with less than 12 months of follow-up in this primary study may be considered on a case-by-case basis at the judgement of the Principal Investigator and after consultation with the Sponsor. In these cases, EOS visit may be conducted anytime when transition to the LTFU study is imminent. Informed consent will be obtained prior to participating in the LTFU Study.

The following assessments and procedures will be performed unless otherwise stipulated:

- Review and record concomitant medications.
- Physical examination.
- Vital signs.
- Assessment of AEs.
- ERT administration log.
- JROM (at Months 18, 24, 30, and 36/EOS only).
- Neurologic cranial nerve exam and muscle strength testing of the upper extremities (at Months 18, 24, 30, and 36/EOS only).
- 12-lead ECG (at Months 18, 24, 30, and 36/EOS only).
- ECHO (at Months 24 and 36/EOS only).
- Clinical laboratory tests.
- Liver panel.
- GAG testing in urine.

- IDS / GAG testing in blood.
- Circulating AFP level (at Months 18, 24, 30, and 36/EOS only).
- PFTs (at Months 18, 24, 30, and 36/EOS only).
- 6MWT (at Months 18, 24, 30, and 36/EOS only).
- Neurocognitive abilities tests by WASI-II, WPPSI-IV, or BSID-III, and by VABS-II (at Months 18, 24, 30, and 36/EOS only).
- MRI of liver (at Months 18, 24, 30 and 36/EOS only).
- MRI of brain and cervical spine (at Months 24 and 36/EOS only).
- Immunogenicity assays (at Months 18 and 24 only).

6.10 Early Termination

Subjects who discontinue from the study prematurely or are withdrawn from the study will be asked to return to the study site for an early termination visit (ETV).

It is at the discretion of the Principal Investigator, in consultation with the Medical Monitor, to waive any procedure if the procedure has been performed within the standard interval of scheduled study visits per protocol.

- Review and record concomitant medications.
- Complete physical exam.
- Vital signs.
- Assessment of AEs.
- ERT administration log.
- JROM.
- Neurologic cranial nerve exam and muscle strength testing of the upper extremities.
- 12-lead ECG.
- ECHO.
- Clinical laboratory tests.
- Liver panel.
- GAG testing in urine.
- IDS / GAG testing in blood.
- Circulating AFP level.
- PFTs.
- 6MWT.
- Neurocognitive abilities tests by WASI-II, WPPSI-IV, or BSID-III, and by VABS-II.

- MRI of liver.
- MRI of brain and cervical spine.

6.11 ERT Withdrawal (any time after Week 12)

Subjects who are willing and who are at least 12 weeks post administration of SB-913 may be considered for withdrawal of ERT by the Principal Investigator after consultation with the Sponsor. For ERT withdrawal, subjects must be medically stable and agree to increased safety monitoring and lab testing until the ERT Withdrawal Follow-Up visit.

The ERT Withdrawal visit may occur concurrently or independent of a regular scheduled visit.

The ERT Withdrawal visit should be combined with a regular scheduled visit whenever possible to reduce study burden.

The following assessments and procedures will be performed:

- Review and record concomitant medications.
- Complete physical exam.
- Vital signs.
- Assessment of AEs.
- ERT administration log.
- Clinical laboratory tests.
- Liver panel.
- GAG testing in urine.
- IDS / GAG testing in blood.
- PFTs.
- 6MWT.

6.12 ERT Withdrawal Monitoring (ERT Withdrawal Weeks 1, 2, 3, 4, 6, 8, 10, and 12 [+/-2 days])

ERT Withdrawal Monitoring visits will take place on a weekly basis for the first 4 weeks, and on a biweekly basis for the last 8 weeks following the ERT Withdrawal visit until the ERT Withdrawal Follow-Up visit.

ERT Withdrawal Monitoring visits should be combined with regular scheduled visits whenever possible to reduce study burden.

ERT Withdrawal Monitoring visits may be conducted at home if the subject is remote.

- Review and record concomitant medications.
- Assessment of AEs.
- ERT administration log.

- Liver panel.
- GAG testing in urine.
- IDS / GAG testing in blood.

6.13 ERT Withdrawal Follow-Up (up to 12 weeks post-ERT Withdrawal visit)

The ERT Withdrawal Follow-Up visit can occur at any time up to 12 weeks after the ERT Withdrawal visit at the discretion of the Principal Investigator.

- Review and record concomitant medications.
- Complete physical exam.
- Vital signs.
- Assessment of AEs.
- ERT administration log.
- Clinical laboratory tests.
- Liver panel.
- GAG testing in urine
- IDS / GAG testing in blood.
- PFTs.
- 6MWT.
- ERT clinical assessment.

7. INVESTIGATIONAL PRODUCT AND OTHER STUDY MEDICATIONS

7.1 SB-913

SB-913 is a combination of 3 recombinant adeno-associated virus serotype 2/6 (rAAV2/6) vectors that encode:

- ZFN 1 (SB-47171): Left-side ZFN that targets base pairs 447-461 of the albumin locus relative to the transcription initiation site (ZFN 1 product vials are labeled as SB-A6P-ZLEFT).
- ZFN 2 (SB-47898): Right-side ZFN that targets base pairs 468-485 of the albumin locus relative to the transcription initiation site (ZFN 2 product vials are labeled as SB-A6P-ZRIGHT).
- hIDS Donor (SB-IDS): DNA repair template that encodes a promotorless hIDS transgene (hIDS Donor product vials are labeled as SB-A6P-HNT).

Purified lots of recombinant vector are formulated in phosphate buffered saline (PBS) containing CaCl₂, MgCl₂, NaCl, Sucrose & Kolliphor (Poloxamer) P 188, and filled at volumes of either 5 mL or 10 mL into vials, which are then stored at \leq -65°C. The lots are tested for identity, sterility, potency, and stability.

7.1.1 Inventory, Storage, and Handling of the Drug Product

The SB-913 components required for subject treatment will be shipped to the study center with dry ice and temperature monitoring device, and will be required to be stored at \leq -65°C (with temperature monitoring) prior to administration.

A Clinical Certificate of Analysis for each SB-913 component will accompany each shipment. The vials will have a label affixed containing the following information: vector identity, lot number, concentration, volume, storage conditions, manufacturer, date of manufacturing, sponsor, and "Caution: For investigational use only".

Subject-specific kits, comprised of the three SB-913 components in the quantities required based on the subject's weight and cohort will be prepared for shipment to the study center. Kit labels will contain the following additional information: subject ID number, protocol number, and quantity.

The study center is required to maintain complete records of all study products received during the course of this study, as well as of labeled product that is dispensed. At the conclusion or termination of this study, return or destruction of all drug supplies must be coordinated with Sangamo (refer to the Pharmacy Manual for additional details).

The Principal Investigator agrees not to supply labeled product to any person other than study personnel and subjects in this study.

7.1.2 SB-913 Administration

Side effects following SB-913 infusions may include transient fever, chills, and/or nausea. These symptoms can be treated with acetaminophen (Tylenol or Paracetamol) 650 mg by mouth and diphenhydramine hydrochloride (Benadryl) 25-50 mg by mouth or IV or equivalent medication. These medications may be repeated every 3-4 hours as needed.

SB-913 will be shipped to the study site prior to the scheduled infusion.

On Day 0, after the subject has arrived at the hospital or acute care facility and has been confirmed to be eligible for infusion, the three SB-913 rAAV2/6 vector components (ZFN1, ZFN2, and hIDS Donor) will be thawed by placing the vials at room temperature. Then each component will be added to 200 mL of diluent (refer to the Pharmacy Manual) and adjusted to 0.25% human serum albumin. Total infusion volumes will be calculated according to a subject's cohort assignment and body weight (kg). Once the SB-913 infusion is prepared it should be transported at room temperature to the infusion facility at the hospital or acute care facility, and be kept at room temperature prior to infusion. SB-913 will be infused while monitoring the subject's vital signs (temperature, heart rate, respiratory rate, and blood pressure) pre-, during, and post-infusion until discharge (for frequency, refer to the Study Reference Manual).

For detailed instructions for thawing and infusing SB-913, refer to the Pharmacy Manual.

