4. SUBJECT SELECTION

4.1 Inclusion Criteria

Subjects must meet all of the following criteria to be included in the study:

- 1. Signed informed consent.
- 2. \geq 5 years of age:
 - a) Adult cohorts 1 through $4: \ge 18$ years of age;
 - b) Pediatric cohorts 5 and 6: 12 to 17 years of age; and
 - c) Pediatric cohorts 7 and 8: 5 to 11 years of age.
- 3. Clinical diagnosis of MPS II (based on evidence of hepatosplenomegaly, dysostosis multiplex by X-ray, valvular heart disease, or obstructive airway disease); IDS deficiency confirmed by gene sequencing.
- 4. Sexually mature subjects must agree to use a barrier contraceptive method for prevention of AAV transfer as follows: for female subjects this means that the subjects' partners must use a condom from dosing with SB-913 until at least 3 consecutive plasma samples after administration of SB-913 are negative for AAV2/6; for male subjects this means that the subjects must use a condom and must refrain from sperm donation from the time of SB-913 administration until at least 3 consecutive semen samples after administration of SB-913 are negative for AAV2/6. Additionally, female subjects of child-bearing potential must consent to use a highly effective method of contraception.
- 5. Magnetic resonance imaging (MRI) negative for liver mass as read by a radiologist.

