4.2 Exclusion Criteria

Subjects who meet any of the following criteria will be excluded from participating in the study:

- 1. Known to be unresponsive to ERT.
- 2. Neutralizing antibodies in serum (immune response) to AAV2/6.
- 3. Serious intercurrent illness or clinically significant organic disease (unless secondary to MPS II) such as cardiovascular, hepatic, pulmonary, neurologic, or renal disease.
- 4. Receiving antiviral therapy for hepatitis B or C, or with active hepatitis B (HBV DNA positive or HBV surface antigen positive) or hepatitis C (HCV RNA viral load) or human immunodeficiency virus (HIV)-1/2 (HIV RNA viral load or HIV antibody positive); to be considered negative for hepatitis C after treatment of an active HCV infection, viral assays in 2 samples collected at least 6 months apart must be negative.
- 5. Lack of tolerance to idursulfase treatment with significant infusion-associated reactions (IARs) or occurrence of anaphylaxis.
- 6. Polymorphisms in the ZFN-targeted region of the albumin locus.
- 7. Liver fibrosis score of 3 or 4 on a 0 to 4 point scale (Desmet et al. 1994) if subject has had a liver biopsy within 2 years of Screening.
- 8. Markers of hepatic dysfunction as evidenced by one or more of the following:
 - a) Platelet count $<100,000/\mu$ L

- b) Albumin $\leq 3.2 \text{ g/dL}$
- c) Total bilirubin >1.5 x upper limit of normal (ULN) and direct bilirubin ≥0.5 mg/dL
- d) Alkaline phosphatase >2.0 x ULN
- e) ALT or AST > 2.0 x ULN
- 9. Creatinine $\geq 1.5 \text{ mg/dL}$.
- 10. Weight < 20 kg at Screening visit.
- 11. Pregnant or breastfeeding female.
- 12. Contraindication to the use of corticosteroids.
- 13. Current treatment with systemic (IV or oral) immunomodulatory agent or steroid use (topical treatment allowed, e.g., for asthma or eczema).
- 14. History of active malignancy in past 5 years (non-melanoma skin cancer or cervical cancer *in situ* permitted).
- 15. Participation in prior investigational drug or medical device study within the previous 3 months.
- 16. Prior treatment with a gene therapy product.
- 17. History of alcohol or substance abuse that in the opinion of the Principal Investigator may interfere with study compliance.
- 18. History of therapeutic non-adherence.
- 19. Elevated or abnormal circulating α -fetoprotein (AFP).
- 20. Any other reason that, in the opinion of the Principal Investigator or Medical Monitor, would render the subject unsuitable for participation in the study.

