6. STUDY METHODOLOGY

Prior to initiation of this study, the study site shall be approved by the IRB/IEC or equivalent. Subjects must be willing to participate in all study procedures related to this protocol. The following sections describe all study procedures. Additional detailed instructions will be provided in the Study Reference Manual, Laboratory Manual, and Pharmacy Manual. A table of all study procedures is presented in the Schedule of Events (see Appendix 1).

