9.3 Concomitant Medications

Current concomitant medications will be recorded. For details, refer to the Study Reference Manual.

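### Section 7.1.2 gives one fixed symptomatic regimen with no weight adjustment or daily maximum, although children from age 5 and 20 kg may enrol

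*Protocol*

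**What the plan says.** Protocol Section 7.1.2 names transient fever, chills and nausea as possible side effects of the infusion and then gives the treatment: "These symptoms can be treated with acetaminophen (Tylenol or Paracetamol) 650 mg by mouth", plus diphenhydramine 25-50 mg by mouth or IV, or an equivalent medicine. On repeats it says only: "These medications may be repeated every 3-4 hours as needed". The section does not distinguish cohorts, ages or weights, and it limits neither the number of doses nor the daily amount.

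Eligibility reaches well below adult size. Section 4.1 includes "Pediatric cohorts 7 and 8: 5 to 11 years of age", and the only weight criterion, in Section 4.2, is the exclusion "Weight < 20 kg at Screening visit".

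In the text available, no other section gives a dose for either drug. Section 7.2 mentions both, but only to say that their use must be recorded. The closing reference in Section 7.1.2 is about the study product: "For detailed instructions for thawing and infusing SB-913, refer to the Pharmacy Manual".

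**The concern.** The paragraph reads as adult guidance that was carried into a protocol with four pediatric cohorts. Because no cohort is excepted, the natural reading is that the printed doses apply to all of them. A clinician who uses the printed dose for a child near 20 kg gives about three times the per-kilogram amount that a 60 kg subject receives, and nothing in the section says when to stop repeating.

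The protocol scales by weight elsewhere. SB-913 is dosed in vg/kg, Appendix 3 doses prednisone by weight band and in mg/kg below 30 kg, and Sections 9.12 and 9.31 limit pediatric blood draws to 0.8 mL/kg in 24 hours. Liver function is also the most closely watched safety signal. Section 9.13 advises subjects against liver-toxic medicines for a year after the infusion, but it does not say how acetaminophen is to be regarded.

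What is at stake is the safety of the lightest children. No endpoint, sample size or analysis depends on it.

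**Working it through.** The plan has no figure of its own to reproduce here. The check is a reading of the text followed by simple division.

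**Inputs**
- Acetaminophen 650 mg per dose; diphenhydramine 25-50 mg per dose; repeat interval 3 to 4 hours (Section 7.1.2).
- Lowest eligible weight 20 kg (Section 4.2).
- Comparison weights of 30, 40 and 60 kg are illustrative. The documents give no weights by cohort.

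**Formulas**
- Per-dose exposure = dose / weight.
- Largest number of doses in 24 hours = 24 / interval, which is 24/4 = 6 or 24/3 = 8.
- 24-hour exposure = dose × number of doses / weight.

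**Results**

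| Weight (kg) | Acetaminophen per dose (mg/kg) | Diphenhydramine per dose (mg/kg) | Acetaminophen over 24 h if every repeat is given (mg/kg) |
|---|---|---|---|
| 20 | 650/20 = 32.5 | 1.25-2.5 | 195-260 |
| 30 | 650/30 = 21.7 | 0.83-1.67 | 130-173 |
| 40 | 650/40 = 16.3 | 0.63-1.25 | 97.5-130 |
| 60 | 650/60 = 10.8 | 0.42-0.83 | 65-87 |

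- Ratio of 20 kg to 60 kg: 32.5/10.8 = 3.0.
- One dose at 20 kg equals three doses at 60 kg per kilogram: 3 × 650/60 = 32.5 mg/kg.
- With a single repeat (two doses, 1,300 mg): 1,300/20 = 65 mg/kg at 20 kg against 1,300/60 = 21.7 mg/kg at 60 kg.
- Total amount over 24 hours, the same at every weight: 6 × 650 = 3,900 mg to 8 × 650 = 5,200 mg.

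The per-dose figures need no assumption about repeats. The 24-hour figures are a worst case: the text allows round-the-clock repetition but does not require it.

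**Number of subjects.** The lightest children are mainly in Cohorts 7 and 8. At two per cohort that is 4 of 16 base subjects. With about two more in every cohort it is about 8 of 32. Both counts assume that these cohorts open at all; their doses are still to be decided.

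**The case against.** The strongest reply is that nothing here is mandated. The symptoms can be treated with these drugs or an equivalent, repeated as needed, so a clinician who gives a child a weight-appropriate dose complies fully with the section. The setting also limits the risk, since Section 6.4 has subjects "remain there for at least 24 hours after the infusion for observation". That the regimen covers every cohort is inferred from silence. Dosing limits may also exist elsewhere. Section 6 says: "Additional detailed instructions will be provided in the Study Reference Manual, Laboratory Manual, and Pharmacy Manual". Section 9.3 says: "Current concomitant medications will be recorded. For details, refer to the Study Reference Manual". Those manuals were not available, and part of the protocol text between Sections 7.2 and 8.1.1 was missing from the copy reviewed. Finally, the documents state no safe mg/kg limit, so dividing a fixed dose by a smaller weight does not by itself show harm, and the 24-hour totals combine several worst-case assumptions.

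Most of this stands, and it bounds the point: this is incomplete guidance, its clinical consequence cannot be quantified from the documents, and a manual may already close the gap. It does not remove the point. The permissive wording leaves open whether to treat and with which drug, but it does not tell staff that the only printed dose is unadjusted for a 20 kg child. Inpatient observation helps detect a problem, but doses given for early infusion symptoms would fall within that same period. Section 7.1.2 does not direct the reader to any manual for these drugs.

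One point on timing is fair. Section 1.5 records that the Safety Monitoring Committee had already recommended opening Cohort 5, so the text may be corrected too late for some subjects aged 12-17. For most of that group the concern is smaller.

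**Conclusion.** The concern holds and the text should be fixed. As printed, the regimen gives a child at the eligibility floor 32.5 mg/kg of acetaminophen per dose, three times the amount at 60 kg, and diphenhydramine 1.25-2.5 mg/kg against 0.42-0.83 mg/kg, with no stated limit on repeats for anyone.

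This rests on three assumptions: that the absence of a cohort restriction means the paragraph applies to Cohorts 5-8; that a child near 20 kg is enrolled; and that staff use the printed dose. It states the exposure that the text permits, not that a toxic level is reached. Confidence is medium, because the unseen manuals may already contain limits.

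**What to change.** In Section 7.1.2, restrict the fixed doses to adult Cohorts 1-4, add a maximum daily dose for all subjects, and require weight-based dosing with a daily maximum for Cohorts 5-8. The sponsor's clinicians should set the values. If a manual already contains them, an explicit cross-reference from Section 7.1.2 is enough. The per-kilogram, 24-hour form used for pediatric blood draws in Section 9.12 can serve as the model.

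The change should be in force before pediatric dosing and, if Cohort 5 has already opened, at the latest before Cohorts 7 and 8. Section 11.3 leaves time for that: the younger children are dosed only after older children have been dosed at the same level and the committee has reviewed at least 4 weeks of their safety data.

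The cost is two or three sentences, or one cross-reference, in a protocol amendment with the usual approvals under Sections 14.2 and 14.3. It adds no visits, procedures or data collection and leaves the endpoints and analyses unchanged.
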